• A non-mydriatic fundus camera will be used to diagnose diabetic retinopathy, glaucoma and macular degeneration, to analyze the retina of healthy individuals and to enable specialist physicians to diagnose diseases from fundus images. This camera allows detailed visualization of the vessels and retinal structure at the bottom of the eye by taking high-resolution retinal photographs. The cleaning of optical components will be

Document No	TF.01.CIP.01
Issue Date	01.05.2023
Revision No	V.00
Revision Date	N=1

done regularly by hospital staff.

• Retinow AI software: Retinow software will be used by retina specialists to evaluate fundus images and compare results for clinical validation of the Retinow AI device. Retinow AI is an artificial intelligence-based software that diagnoses eye diseases by analyzing fundus images. The computer systems on which the software runs will be checked regularly, virus scans and security updates will be made. The analysis results of the software will be compared periodically with the results of specialist ophthalmologists. Since the latest version of the Retinow AI software will be used, no changes will be made to the software during the clinical study.

The clinical study protocol will be carried out in the following steps:

- 1. Participant Selection: Participants who apply to the retina and glaucoma clinic and meet the study inclusion and exclusion criteria will be determined by the specialist physicians in the study.
- 2. Information and Consent: Participants who meet the eligibility criteria will be provided with detailed information about the study and written informed consent will be obtained from them. The content of the informed consent form is arranged in accordance with the relevant integrity and data protection legislation. In the volunteer information and the informed consent form, the volunteer will be fully informed about how the clinical trial data will be collected, used and published.
- 3. Imaging Directions: Participants will be directed to the fundus imaging room by a specialist doctor for fundus photography. Retinal patients diagnosed with diabetic retinopathy, glaucoma, and macular degeneration will be sent for color fundus photography after the initial diagnosis examination. Similarly, healthy participants with no pathological findings in their retinas will be sent for a control fundus photography.

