- 4. Fundus Photography: In this study, no invasive procedure will be applied to the patient, and the retinal photography will be taken by the camera operator with a special non-mydriatic digital camera called a fundus camera. In some patients diagnosed with Retinow AI, pharmacological dilatation (mydriasis) using a dilatation solution may be required to obtain a fundus image of sufficient quality. The dilatation procedure will be performed only by healthcare personnel (general practitioners, nurses, etc.) who are competent and trained in this regard.
- 5. Recording of Images: Right and left fundus images of each participant will be taken and these images will be recorded by the responsible researcher. The principal investigator will download the images via the hospital's PACS system.
- 6. Analysis of Images: Fundus photographs will be analyzed by the Retinow AI device. Then, they will be analyzed by expert ophthalmologists for gold standard evaluation.

Revision Date	920	
Revision No	01.05.2023 V.00	
Issue Date		
Document No	TF.01.CIP.01	

8. Gold Standard Assessment: The gold standard assessment results performed by specialist doctors will be used to determine the sensitivity and specificity of the Retinow Al device.

Al Analysis: Retinow Al software will analyze the collected images within 24 hours of image acquisition. This rapid analysis will allow for a near real-time comparison with expert diagnoses.

Clinical data will be fed into Retinow Al software and the success metrics (Accuracy, Sensitivity, Specifity) will be evaluated. Diagnostic labels provided by Retinow Al software will be compared with labels provided by expert ophthalmologists. Performance metrics of accuracy, sensitivity and specificity will be calculated.

The clinical study will be completed when the predicted number of data is reached

9. Subjects

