9.2. Exclusion Criteria

Volunteers who do not want to have fundus imaging
Cases that do not comply with fundus photography for any reason
Patients with conjunctival and corneal infections,
People with hereditary or congenital retinal diseases,
People with cataracts,
People with uveitis,
Patients with permanent visual impairment in one or both eyes,
Patients with correction of + 6D and above – 6D,
Pregnant

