ANNEX 1.

STATISTICAL ANALYSIS PLAN

Analysis Population and Procedures

Analyses will be performed on a Per Protocol (PP) basis only. The PP analysis will include participants who completed the study per protocol and this population will accurately reflect the effectiveness and reliability of the software in diagnosing diabetic retinopathy, glaucoma and macular degeneration.

Baseline Data and Endpoints Descriptive Statistics

Baseline Data:

Baseline data includes the age and gender information of all patients participating in the clinical study. This data does not affect the results of the Retinow AI software. It will only be collected to obtain information about the age and gender distribution.

Endpoints Descriptive Statistics:

Endpoints are the sensitivity, specificity and accuracy rates of the Retinow Al software in diagnosing diabetic retinopathy, glaucoma and macular degeneration diseases. These rates show how well the software agrees with the diagnoses made by specialist physicians. Descriptive statistics are used to measure these rates. The definitions of these rates are provided below.

Sensitivity: The ability of the software to correctly identify individuals with the disease. High sensitivity reduces the probability that the software will miss signs of the disease. (True positive rate).

Specificity: The ability of the software to correctly identify healthy individuals. High specificity minimizes false positive results. (True negative rate).

Accuracy: It is defined as the percentage of correct results in all diagnoses of the software.

These descriptive statistics will be used to further evaluate the reliability, effectiveness, and usability of the Retinow Al software in clinical applications.

Analytical Procedures

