The comparisons of the diagnosis of disease results in the clinical trial by the doctor and the Retinow Al software will be examined. The results will be analyzed with Cohen's Kappa analysis. The parameters to be analyzed are sensitivity, specificity and accuracy values. Sensitivity is defined as the accuracy between positive findings according to the clinical reference standard; It will be calculated as the ratio of eyes with positive findings according to the reference standard and positive results with the Retinow Al system. Specificity is defined as the accuracy between negative findings according to the clinical reference standard; It will be calculated as the ratio of eyes with negative findings according to the reference standard and negative results with the Retinow Al system. (Positive findings indicate being sick, negative findings indicate being healthy)

Statistical analyses will be performed using the Python programming language version 3.11.4 and the TensorFlow library version 2.10.0. In addition to these calculations, the Cohen's Kappa method will also be used for the analysis of the results. These analyses involve the use of the specified software versions and tools in the data processing and model building stages. This process aims to specify the relevant software and versions to ensure the reliability and framework of the research results. Considering the referenced cases as 'positive' and the non-referenced cases as 'negative', the sensitivity, specificity and accuracy scores are clinically significant measurements and will be calculated with 95% confidence intervals. For each disease, tables will be created to compare the sensitivity and specificity of the algorithm with the reference standard. The reference standard is defined as the majority decisions of the ratings of 3 expert ophthalmologists. The definitions of the positive and negative cases to be analyzed are given below.

Document No	TF.01.CIP.01
Issue Date	01.05.2023
Revision No	V.00
Revision Date	120

		Retinow AI				
		Disease	No Disease	Total	Kappa	p
Doctor	Disease	TP	FN			
	No Disease	FP	TN			
	Total					

Kappa Score: Cohen's Kappa score is a statistical method used to measure the agreement between two raters or observers. It shows how much the two parties agree, taking into account the probability of random agreement.

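### Sensitivity and specificity rest only on eyes that were imaged successfully, and no planned analysis shows how far the 90% pass criteria depend on that selection

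*Combined protocol and SAP*

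**What the plan says.** **Order of events (Section 8, step 3).** Disease status is known before the photograph is taken. Diagnosed patients "will be sent for color fundus photography after the initial diagnosis examination", and "healthy participants with no pathological findings in their retinas will be sent for a control fundus photography".

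**Imaging (Section 8, steps 4 and 5).** The camera is non-mydriatic. For some patients, "pharmacological dilatation (mydriasis) using a dilatation solution may be required to obtain a fundus image of sufficient quality". Both eyes are photographed: "Right and left fundus images of each participant will be taken".

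**Exclusion (Section 9.2).** The second criterion removes "Cases that do not comply with fundus photography for any reason".

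**Stopping (end of Section 8).** "The clinical study will be completed when the predicted number of data is reached".

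**Analysis (Annex 1).** "Analyses will be performed on a Per Protocol (PP) basis only". Rates are computed over eyes. For sensitivity, "It will be calculated as the ratio of eyes with positive findings according to the reference standard"; specificity is built the same way on reference-negative eyes. The table of physician against software has two outcomes for the software, disease or no disease.

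**Pass rule and losses (Annex 1).** Accuracy, sensitivity and specificity must each reach 90% for all diseases. Technical errors and data loss must stay below 10%; no denominator and no split by group is given. The sample size text plans 305 people per disease, with a margin for lost data and lost participants.

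**The concern.** An eye that cannot be photographed adequately has no place in the two-by-two table and no place in the analysis set. What remains is a set of eyes selected for successful imaging. If the software would read the lost eyes less well than the kept ones, the per-protocol rate is too high for the eyes presented to it. If it would read them equally well, nothing changes. If it would read them better, the rate is too low.

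Sensitivity and specificity have separate denominators, so losses among diseased eyes affect only the first and losses among healthy eyes only the second. A single pooled loss figure does not show which rate is exposed. Because the study runs until the intended number of data is reached, lost cases might also be replaced, so a full final count need not mean that few were lost.

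At stake is an all-or-nothing verdict at 90% on each measure, for a device that Section 4.1 presents as rapid screening and triage without a trained expert. Performance on hard-to-photograph eyes is relevant to that use.

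**Working it through.** **Inputs from the documents:** 305 people per disease and the loss cap below 10% (Annex 1); two eyes photographed per person (Section 8, step 5); 90% thresholds (Annex 1). The stated total is consistent: 3 × 305 = 915.

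**Assumptions, because the documents give no figure:** the share of a group's eyes lost for image reasons (L); the software's performance on lost eyes; the split between diseased and healthy within each 305; and the cap being counted per disease and per eye.

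**1. How much loss the cap allows.** 305 × 2 = 610 eyes per disease. Below 10% means at most 60 lost eyes, and 60/610 = 9.8%.

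**2. Worst-case bound.** If every lost eye counts as an error, rate = per-protocol rate × (1 − L). The last column is the per-protocol rate needed for the bound to stay at 90%, which is 0.90/(1 − L).

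| L in that group | 90.0% becomes | Needed to keep 90% |
|---|---|---|
| 2% | 0.90 × 0.98 = 88.2% | 91.8% |
| 5% | 0.90 × 0.95 = 85.5% | 94.7% |
| 9.8% (60/610) | 0.90 × 550/610 = 81.1% | 99.8% |

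The last row is also the bound for accuracy when the cap is fully used, however the losses are split: a lost eye counted as an error is an error for accuracy in either group.

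**3. What the missing split permits.** Suppose all 60 lost eyes fell in one group. Its loss would be
- 60/305 = 19.7% if it held half of the eyes,
- 60/244 = 24.6% if it held 40%,
- 60/458 = 13.1% if it held 75%,

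with none in the other group and the cap still met. This shows what the rule allows, not what is expected.

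**4. A less extreme calculation.** If the rate is e in kept eyes and d in lost eyes, the rate over all eyes is (1 − L)e + Ld. The per-protocol rate therefore exceeds it by L(e − d).
- L = 5%: gaps of 0, 2, 5 and 10 points give 0, 0.1, 0.25 and 0.5 points.
- L = 10%: the same gaps give 0, 0.2, 0.5 and 1.0 points.
- L = 19.7%: gaps of 2, 5 and 10 points give 0.4, 1.0 and 2.0 points.

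The distance between steps 2 and 4 is the uncertainty that the planned outputs leave open.

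**The case against.** A reader might infer that dilatation is optional, so that hard-to-photograph eyes would be dilated and kept in one group and dropped in the other. The documents do not support that. Step 4 describes one conditional procedure with no separate rule for healthy participants. The natural reading is that dilatation comes first and exclusion only if the image is still inadequate. Unequal handling is neither stated nor shown. The missing trigger is a gap in detail only.

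Other points in the plan's favour:

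- **The exclusion may concern cooperation, not image quality.** It follows the criterion on unwilling volunteers, and eligibility precedes imaging. Applying it to ungradable images is an inference. If the narrower reading is right, however, an ungradable eye still has no cell in the table and no stated treatment in the per-protocol analysis.
- **Text is not visible.** The numbered steps pass from 6 to 8, and Sections 9.3, 10.3, 11 and 13 show headings only. A rule could be there. This stands, and limits the point to the visible text.
- **Causes of poor images are already reduced.** Cataract, uveitis, corneal infection and high refractive error are excluded in everyone. Others, such as small pupils, remain.
- **The ordinary effect is small.** Losses of 5% to 10% with gaps up to 10 points give at most 1.0 point. The 95% half-width for 90% on 305 eyes is 1.96 × √(0.9 × 0.1/305) = 3.4 points if eyes are independent. That is fair on size, but a confidence interval does not cover selection.
- **A failed photograph is not a software error.** The objective is diagnosis from fundus photographs, so scoring lost eyes as errors answers a different question. This stands. It is why the added analysis must be secondary and labelled a bound.
- **Lost eyes have no three-expert reading.** Assigning them by the patient's diagnosis could count a healthy fellow eye as a missed diseased eye. This also stands, and it determines how the fix assigns eyes.

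**Conclusion.** The point holds as a gap in analysis and reporting. On the visible text, per-protocol analysis alone, a two-outcome table and an open-ended photography exclusion applied when disease status is known mean that the rates describe eyes selected for successful imaging. The pooled cap bounds the amount of loss but shows neither where it falls nor what it does to each rate.

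Direction and size are unknown. In the worst case, 90.0% becomes 88.2%, 85.5% or 81.1% at 2%, 5% or 9.8% loss in that group. With gaps of 0 to 10 points and 5% to 10% loss, the shift is 0 to 1.0 point. The loss shares and gaps are assumptions; the 9.8% also assumes a cap counted per disease and per eye. The documents do not show that the groups will be treated differently or that a pass would be wrong. This is a cheap improvement, not a fault that invalidates the design.

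**What to change.** 1. Keep the per-protocol estimate as primary.
2. Record two yes/no items per eye at imaging, dilatation and loss for image reasons, and report both by diseased and healthy group for each disease.
3. Add to Annex 1 one sensitivity analysis, labelled a worst-case bound, that counts eyes lost for image reasons as errors in the eye-level sensitivity, specificity and accuracy. Assign each lost eye as positive or negative by its own diagnosis at the initial examination. Where no eye-level diagnosis exists, show the result under both assignments.
4. As a clarification only, state in Section 8, step 4 when an inadequate first image leads to dilatation, and that the rule is the same for all participants.

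Cost: two data fields, one table and one analysis, with no extra participants or readers. The downside is a possibly less favourable secondary figure. If losses are few and balanced, the table will show it and support the primary result.

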2.3. Research Center Information

Name of research center	Address
Ankara Bilkent City Hospital	[name]
	[name]

Note: No service is received from outside the center regarding the research.

3. General Summary of the Clinical Trial

Background	Eye diseases stand out as a major public health problem worldwide and constitute one of the
	leading causes of vision loss. Diseases such as diabetic retinopathy, glaucoma and macular
	degeneration are among the problems that can seriously affect the quality of life and lead to
	vision loss. Therefore, early diagnosis of these diseases is vital for determining effective
	treatment methods and protecting and improving the quality of life of patients.
	In recent years, artificial intelligence (AI) technologies in the field of medicine have offered
	great potential in disease diagnosis and management. Artificial intelligence algorithms,
	especially those used for retinal image analysis, play an important role in the early diagnosis of
	eye diseases and the determination of treatment methods. The use of artificial intelligence in
	the field of ophthalmological clinical research is mostly related to the prediction and diagnosis,
	treatment and interventions, and prevention and management of ophthalmic diseases. In this
	context, ophthalmic imaging and early screening systems supported by artificial intelligence
	technology play an effective role in the diagnosis of diseases such as diabetic retinopathy,
	glaucoma and macular degeneration.
	Diabetes is a major global health problem with an estimated 463 million people living with
	diabetes worldwide. This number is expected to increase to 700 million by 2045 [1]. Diabetic
	retinopathy (DR), a common complication of diabetes, is considered the leading cause of new-
	onset blindness among adults aged 20–74 years [2]. As the prevalence of diabetes continues to
	increase, the global DR patient population is projected to increase to 160 million by 2045 [1].
	Early diagnosis and timely treatment of DR can reduce 95% of blindness from this cause [3].
	Therefore, DR screening programs are recommended for patients with diabetes by the World
	Health Organization [4].
	Glaucoma is characterized by optic disc cupping and visual field distortion, and is the most
	common cause of irreversible blindness, affecting more than 70 million people worldwide [5,7].

Document No	TF.01.CIP.01
Issue Date	01.05.2023
Revision No	V.00
Revision Date	:=:

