4.12. Working Principle of the Device

The working principle of the Retinow AI system is as follows.

- The user logs in to retinow.com.tr.
- The user login on the site enters the system with the license given by Retinow Al.
- Through the cloud system in Retinow AI, the user uploads patient information and fundus images of the patient to the system.
- Retinow Al analyzes the uploaded fundus images and presents them to the user in the form of a detailed report.
- The user can follow up the patient from the system. Can examine images in detail and keep records.

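### Section 8 and Annex 1, as far as visible, do not require the three reference graders to be masked to the software output or their grades to be locked before comparison

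*Combined protocol and SAP*

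**What the plan says.** Section 8, step 6 (Analysis of Images) sends the photographs to the software and continues: "Then, they will be analyzed by expert ophthalmologists for gold standard evaluation". Step 8 uses those expert results to determine sensitivity and specificity.

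The methods-and-tools part of Section 8 adds that "Retinow software will be used by retina specialists to evaluate fundus images and compare results", for the purpose of clinical validation, and that "The analysis results of the software will be compared periodically with the results of specialist ophthalmologists". The AI Analysis paragraph gives the software 24 hours from image acquisition and says: "This rapid analysis will allow for a near real-time comparison with expert diagnoses".

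Annex 1 (Analytical Procedures) defines the reference standard as the majority of three expert ophthalmologists' ratings. It says nothing about what those experts may see when they rate, whether they rate separately, or when a rating becomes final. The software passes only with 90% accuracy, 90% sensitivity and 90% specificity for all diseases.

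The numbering in Section 8 goes from step 6 to step 8. Sections 10.3 (factors that may compromise results) and 11 (data management) show headings only.

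**The concern.** The expert grade is the yardstick for every pass criterion, and for kappa as well. If a grader knows the software's answer, a borderline image may be graded to agree with it. Each majority grade that moves this way turns a false negative into a true negative, or a false positive into a true positive. The error therefore runs in one direction, towards passing, with no gain in real performance.

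The final 2x2 tables would not reveal it, because a moved grade looks like ordinary agreement. A masked re-read of the stored images could repair it afterwards, but only by repeating the grading.

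Reading order alone is not the fault: software-first is harmless if graders are masked. What makes the silence matter is its combination with specialists using the software and comparisons made while the study is running.

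**Working it through.** **Plan figures.** 3 diseases x 305 people = 915, which matches the stated total. No stated figure depends on masking. The visible text does not give the inputs to the kappa calculation behind 305, so that calculation cannot be reproduced.

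**Inputs.** Pass mark 0.90 for each of three measures (Annex 1). The rest are assumptions, because the documents give no value for them:
- q: the disease share.
- t: true sensitivity = true specificity, meaning performance against a masked three-expert majority.
- f: the share of disagreements whose majority grade moves to the software's call, the same for false positives and false negatives.

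**Before movement:** TP = qt, FN = q(1-t), FP = (1-q)(1-t), TN = (1-q)t.

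**After movement:** TP + f·FP, FN(1-f), FP(1-f), TN + f·FN.

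**Direction.** FN to TN lowers FN and raises TN. FP to TP lowers FP and raises TP. With Sensitivity = TP/(TP+FN) and Specificity = TN/(TN+FP), either move raises both (unless already 100%), and it raises accuracy.

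**Accuracy alone.** t + f(1-t) = 0.90 gives f = (0.90-t)/(1-t).
- t = 0.85: 0.05/0.15 = 0.333
- t = 0.88: 0.02/0.12 = 0.167

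**All three marks.** For q of 0.5 or more, sensitivity is the last to reach 0.90. Solving TP + f·FP = 9·FN(1-f) gives f = (9FN - TP)/(FP + 9FN). Results for q below 0.5 mirror these, through specificity.

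| q | t = 0.85 | t = 0.88 |
|---|---|---|
| 0.50 | 0.333 | 0.167 |
| 0.25 or 0.75 | 0.357 | 0.179 |
| 0.10 or 0.90 | 0.366 | 0.183 |
| 0.05 or 0.95 | 0.368 | 0.184 |

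Example, t = 0.85 and q = 0.75: TP 0.6375, FN 0.1125, FP 0.0375, so f = (1.0125 - 0.6375)/(0.0375 + 1.0125) = 0.357. At f = 1/3 the accuracy is 0.900 but sensitivity is only 0.65/0.725 = 0.897, so the accuracy-only figure is slightly too small.

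**One-way movement.** Suppose graders follow only software positives (FP to TP), or only software negatives (FN to TN), and every such disagreement moves.
- From 85%/85% and q = 0.5, following positives only: sensitivity = (0.425 + 0.075)/(0.5 + 0.075) = 0.870, still short.
- From 85%/85% at q = 0.25, 0.50 or 0.75, in either direction, the lowest of the three measures is 0.857 to 0.897. All three marks are never reached.
- From 88%/88% at q = 0.5, the lowest is 0.893, also short. At q = 0.25 (positives only) or q = 0.75 (negatives only) all three are reached, but only at f = 0.56.

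**Unequal errors.** With true sensitivity 82% and specificity 92% and equal two-way movement, f is 0.25 at q = 0.05, 0.34 at 0.10, 0.43 at 0.25, 0.47 at 0.50 and 0.49 at 0.75. Whether unequal errors need more or less movement depends on prevalence.

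**Effect of the majority rule.** If each opposing grader switches independently with probability p, a unanimous vote is overturned with probability 3p² - 2p³. For f = 1/3 this needs p = 0.39. A 2-1 vote against the software is overturned with probability 1 - (1-p)², which needs p = 0.18. The majority rule protects in part, least where experts already disagree.

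**The case against.** The strongest reply is that the plan may already contain the rule. Step 7 would stand between image analysis and gold standard assessment and is not visible; nor is the text of Sections 10.3 and 11. That stands, so the point can be pressed only against the text that can be read. Annex 1 is where the reference standard is defined, and it neither states nor cites masking.

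A reader might go further and infer that the graders will work with the software's report in front of them. The documents do not support that:
- Section 4.12 says the software "analyzes the uploaded fundus images and presents them to the user in the form of a detailed report" and that the user "Can examine images in detail and keep records". This describes the device in general, not this study's grading. Section 8, step 5 has the principal investigator download images through the hospital PACS, so images exist outside the software.
- The text shows that retina specialists use the software, not that they are the three graders. The sentence may describe the validation comparison only.
- Section 2.3 says "No service is received from outside the center regarding the research". Staff of one centre can still be masked, so this is no evidence of exposure.
- The near real-time comparison is with expert diagnoses, which could mean the enrolment diagnoses: patients "will be sent for color fundus photography after the initial diagnosis examination". Those are not the Annex 1 reference.
- Comparing software labels with expert labels, and speaking of three ratings, reads naturally as labels produced separately.

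All of this reduces the claim to an unstated safeguard. It does not supply the safeguard.

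**Conclusion.** The point holds as a missing safeguard, not as a documented exposure. As written, the visible plan permits unmasked reference grading, and any resulting bias would favour passing on all three criteria.

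Its size cannot be estimated from the documents. Under equal true sensitivity and specificity, equal two-way movement and a disease share of 5% to 95%, about 17% to 18% of disagreements must move to lift true 88% to all three marks, and 33% to 37% to lift true 85%. These are scenarios. It would be wrong to infer that any deference to the software produces a pass: one-way movement from 85%/85% does not reach all three marks at a disease share of 25% to 75%. The risk is therefore greatest for software that falls just short of 90%. The separate limit on technical errors and data loss is not affected.

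This is a cheap improvement, worth making before grading starts.

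**What to change.** In Section 8, step 6 and in the Annex 1 definition of the reference standard, state that:

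1. the three experts grade coded images independently and masked to the software output;
2. each grade is locked before the software result for that image is released to any grader;
3. the periodic and near real-time comparisons use only locked grades and are withheld from the graders until all grading is complete.

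If such a rule already exists in text not visible here, cite it in both places instead.

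The cost is a few sentences. The three graders, the images, the sample size, the reading order and the 24-hour software run are unchanged. The downside is that graders cannot see software reports or running comparisons until grading ends.
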